3.3.2 Vital Signs, Physical Examination, and Other Observation Items Related to Safety

3.3.2.1 Vital Signs

Analysis set: Safety analysis set

Analysis variables: Systolic blood pressure
Diastolic blood pressure
Pulse

Visits: Weeks -6, -2, 0, 2, 4, 8, 12, 16, 20, 24, 28, 32, 36, 40, 44, 48, 52, and 54

Analysis methodology: The following analysis will be provided for the above analysis variables by treatment group.

- (1) Summary statistics for each visit and summary statistics for change from Week 0 at each visit after Treatment Period I
- (2) Case plots

3.3.2.2 12-lead ECG

Analysis set: Safety analysis set

Analysis variables: Heart rate

RR interval	
PR interval	
QRS interval	
QT interval	
QTcF interval	
Findings of 12-lead ECG	[Within normal limits, Abnormal but not clinically significant, Abnormal and clinically significant]
Visits:	Weeks -6, 0, 4, 12, 24, 36, 52, and 54
Analysis methodology:	
The following analyses of (1) to (3) will be performed for the above analysis variables except for findings of 12-lead ECG by treatment group.
 
The following analyses of (4) will be performed for findings of 12-lead ECG by treatment group.
 
When the analysis of MAV is performed, if both “upper” and “lower” criteria in the MAV Criteria are applicable to the same test item, the analysis will be performed for each criterion separately.
 
See Appendix 2 of this SAP for the definitions of test items subject to this analysis and the MAV Criteria.
 
 (1) Summary statistics for each visit and summary statistics for change from Week 0 at each visit after Treatment Period I (2) Case plots (3) Frequency distributions for MAV before the start of the study drug administration for Treatment Period II and after the start of SYR-472 25 mg tablet (4) Shift tables showing at Week 0 and each visit after Treatment Period I

3.3.2.3 Hypoglycemia

Analysis set:	Safety analysis set
Analysis variables:	Hypoglycemia that occurs after the start of the study drug administration and before the start of the study drug for Treatment Period II
Analysis methodology:	Hypoglycemia that occurs after the start of SYR-472 25 mg tablet
	The following summaries will be provided for the above analysis variables using frequency distributions in subjects who

concomitantly received insulin preparations among the safety analysis set by treatment group.

In the analysis of hypoglycemia occurring after the start of SYR-472 25 mg tablet, subjects who concomitantly received insulin preparation and SYR-472 25 mg tablet in the safety analysis set will be included in the analyses.

- (1) All hypoglycemia
- (2) Severe hypoglycemia
- (3) Symptomatic hypoglycemia
- (4) Asymptomatic hypoglycemia
- (5) Probable symptomatic hypoglycemia
- (6) Relative hypoglycemia

The frequency distributions will be provided according to the rules below:

[Number of subjects]

A subject with multiple occurrences of hypoglycemia within the same classification will be counted only once in that classification.

[Number of events]

For each summary, the total number of events will be calculated.

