In Study 101, the elimination half-life (mean) of unchanged SYR-472 following the administration of SYR-472 50 mg under fasted conditions (without breakfast) to patients with severe renal impairment and end-stage renal failure was 88.45 and 107.97 hours, respectively, which were longer than those in matched healthy adults (56.43 and 56.75 hours). Based on these results, the time of assessment at the end of the follow-up period was set at Week 54 by reference to 5 times the elimination half-life (18.4 and 22.5 days, or longer) from the last administration of SYR-472 25 mg tablets (Week 51).

(4) Justification for the primary endpoints

According to “the Guideline for Clinical Evaluation of Hypoglycemic Agents (Revised Draft)” [4], HbA1c should be used as an efficacy endpoint in phase 3 studies in principle. In addition, the safety of the study drug should be used as the primary endpoint in long-term studies. Therefore, HbA1c at the end of Treatment Period I will be evaluated as the efficacy endpoint and AEs throughout the treatment period will be evaluated as the safety endpoint.

(5) Justification for the secondary endpoints

In reference to “the Guideline for Clinical Evaluation of Hypoglycemic Agents (Revised Draft)” [4] and based on the results of clinical studies of SYR-472 conducted so far, HbA1c, fasting blood glucose, and glycoalbumin were set as efficacy endpoints, and vital signs, 12-lead ECG, and clinical laboratory test values were set as safety endpoints to evaluate the efficacy and safety of SYR-472 25 mg.

(6) Justification for the inclusion criteria

See Section 7.1.

(7) Justification for the exclusion criteria

See Section 7.2.

(8) Justification for the excluded medications and other exclusions

See Section 7.3.

(9) Justification for the sample size

See Section 13.3.

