9.1.21 Self-Monitoring of Blood Glucose

For subjects using insulin preparations, the investigator or sub-investigator should explain the method of self-monitoring of blood glucose to subjects at the end of the screening period (Week 0), and instruct them to perform self-monitoring of blood glucose using a finger-stick sampling method in the following occasions:

- (1) At scheduled monitoring
 - i) 57
 - ii) From the end of the screening period (Week 0) to Day 7 of administration of the study drug for Treatment Period II, self-monitoring of blood glucose should be performed every day before breakfast prior to administration of the study drug and insulin preparation.
 - iii) From Day 8 of administration of the study drug for Treatment Period II to the end of the follow-up period, self-monitoring of blood glucose should be performed at least once weekly before breakfast prior to administration of the study drug and insulin preparation.
- (2) In case any hypoglycemic symptom occurs

If case any hypoglycemic symptom (e.g., unusual hunger, weakness, finger tremor, cold sweat, or palpitations) occurs, self-monitoring of blood glucose should be performed at the time of its development (prior to treatment for hypoglycemia, if any) and disappearance.

If the blood glucose in self-monitoring is 70 mg/dL or less, presence or absence of hypoglycemic symptoms should be confirmed and recorded in the eCRF along with the blood glucose value (refer to Section 9.1.22).

The investigator or sub-investigator will record all applicable blood glucose values in the eCRFs, and report whether the case is significant hypoglycemia or not. If the case is significant hypoglycemia and treatment is required, the contents of treatment should be recorded in the eCRF.

CCI [REDACTED] (provided by PPD [REDACTED]) should be used as the self-monitoring of blood glucose kit [11][12][13][14].

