 - TEAEs that occur before the start of the study drug for Treatment Period II: The analysis will be performed based on the evaluation result entered in the CRF under “Pretreatment Event/Adverse Event (Period 1).”
 - TEAEs that occur after the start of SYR-472 25 mg tablet: The analysis will be performed based on the evaluation results entered in the CRFs under “Pretreatment Event/Adverse Event (Period 1)” and “Pretreatment Event/Adverse Event (Period 2 and thereafter).” If the

evaluation results differ between “Pretreatment Event/Adverse Event (Period 1)” and “Pretreatment Event/Adverse Event (Period 2 and thereafter),” the evaluation result of “Pretreatment Event/Adverse Event (Period 2 and thereafter)” will be preferentially used.

- Time of onset: In the analysis of TEAEs that occur before the start of the study drug for Treatment Period II, the time of onset will be calculated by defining the day of the start of the study drug administration as day 1. In the analysis of TEAEs that occur after the start of SYR-472 25 mg tablet, it will be calculated by defining the day of the start of SYR-472 25 mg tablet as day 1.
- Number of days from the immediate study drug administration: To be calculated by defining the day of the immediate study drug administration as Day 1. If the study drug administration and TEAE occur on the same day, the number of days from the immediate study drug administration will be defined as 1 day.
- Complications of hepatobiliary disorders: Concurrent medical conditions summarized as hepatobiliary disorders by SOC.
- MAV: An abbreviation for markedly abnormal value.
- Overall hypoglycemia: Hypoglycemia reported as “Yes” for hypoglycemic symptoms and asymptomatic hypoglycemia.
- Asymptomatic hypoglycemia: Hypoglycemia with an evaluable self-monitoring blood glucose value (i.e., non-missing and determined to be eligible based on “Handling Rules for Analysis Data”) and a measured concentration of ≤ 70 mg/dL but determined to be not accompanied by symptoms of hypoglycemia at the measurement of that blood glucose value. The presence or absence of asymptomatic hypoglycemia will be determined for each blood glucose value measured.

HANDLING OF TIME WINDOW

For each test, observation, and evaluation items, evaluable data (i.e., non-missing data and data determined to be eligible based on “Handling Rules for Analysis Data”) will be handled according to the following rules.

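### SAP 3.3.2.3: after-SYR-472 counts of asymptomatic and all hypoglycemia rest on 132 versus 48 scheduled readings per completer; balanced event totals can be recovered by subtraction, subject counts cannot

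*SAP*

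**What the plan says.** **Testing schedule (Protocol 9.1.21, insulin users).** From Week 0 through Day 7 of Treatment Period II drug, "self-monitoring of blood glucose should be performed every day before breakfast". From Day 8 to the end of follow-up, "self-monitoring of blood glucose should be performed at least once weekly before breakfast".

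**Definitions (SAP, list of abbreviations and terms).** Asymptomatic hypoglycemia is an evaluable self-monitored value at or below 70 mg/dL without symptoms, and it is scored reading by reading: "The presence or absence of asymptomatic hypoglycemia will be determined for each blood glucose value measured". The umbrella term, Overall hypoglycemia, is defined as "Hypoglycemia reported as “Yes” for hypoglycemic symptoms and asymptomatic hypoglycemia". The table in 3.3.2.3 labels its first row All hypoglycemia; I read the two labels as the same thing.

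**Table (SAP 3.3.2.3).** Two windows are planned by treatment group:
- from the start of study drug to the start of Treatment Period II drug;
- from the first SYR-472 25 mg tablet onward.

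For subjects the rule is "A subject with multiple occurrences of hypoglycemia within the same classification will be counted only once in that classification"; for events, "For each summary, the total number of events will be calculated". The section gives no time or reading denominator, no row confined to Treatment Period II onward, and no remark on the change in testing. It plans no between-group difference, confidence interval or test.

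**The concern.** An outcome scored at every reading rises with the number of readings. The second window starts at Week 0 for subjects randomized to SYR-472 and at Week 12 for those randomized to placebo, so only the first group's window contains the twelve weeks of daily testing in Treatment Period I. Set side by side, the two columns can suggest that longer or continuous SYR-472 brings more asymptomatic hypoglycemia when only the amount of testing differs.

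The same problem affects a before-and-after reading of the placebo/SYR-472 group. Its counts can fall or rise at the switch without any change in risk, depending on how often subjects test after Day 7 of Treatment Period II.

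Long-term safety is a study objective, and hypoglycemia-related events are of special interest partly because of reports with other DPP-4 inhibitors combined with insulin (Protocol 10.1.5). This is the table that classifies hypoglycemia in insulin users.

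**Working it through.** The documents state no number of readings, so there is no figure of their own to reproduce. The counts below are for a subject who completes follow-up.

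**Calendar.** Treatment Period I lasts 12 weeks (84 days), so Treatment Period II starts on Study Day 85. The last dose is at Week 51 (Study Day 358; Protocol 6.2). The follow-up visit is 21 days later (Protocol 9.3.5), on Study Day 379, which is Week 54.

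**Scheduled readings after the first SYR-472 tablet, minimum schedule.**
- Daily phase: 84 + 7 = 91 in SYR-472/SYR-472; 7 in placebo/SYR-472.
- Weekly phase, Study Day 92 up to the Week 54 visit: (379 - 92)/7 = 287/7 = 41 in both groups.
- Totals: 91 + 41 = 132 against 7 + 41 = 48. Ratio 132/48 = 2.75. Counting one more reading on the Week 54 visit day gives 133/49 = 2.71.

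**If the later phase is tested more often than the minimum.**

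| Readings per week after Day 7 | SYR-472/SYR-472 | Placebo/SYR-472 | Ratio |
|---|---|---|---|
| 1 | 132 | 48 | 2.75 |
| 2 | 91 + 82 = 173 | 7 + 82 = 89 | 1.94 |
| 7 | 91 + 287 = 378 | 7 + 287 = 294 | 1.29 |

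At equal risk per reading, these are also the ratios of expected asymptomatic events from scheduled readings.

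**Subjects with at least one event**, 1 - (1 - p)^n, with n = 132 and 48. The risk per reading p is an assumption; the documents give none.

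| p | Same risk in every subject | Risk varying between subjects (beta, shape 0.1) |
|---|---|---|
| 0.1% | 12.4% vs 4.7% | 8.1% vs 3.9% |
| 0.5% | 48.4% vs 21.4% | 18.6% vs 11.7% |
| 2% | 93.1% vs 62.1% | 29.0% vs 21.8% |

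**What the planned table already allows.** In SYR-472/SYR-472 the Treatment Period I window lies wholly inside the after-SYR-472 window. Subtracting its events leaves those from Treatment Period II onward, which rest on 132 - 84 = 48 readings. That matches the 48 in placebo/SYR-472. Subject counts do not subtract: someone with an event in Treatment Period I is counted once in each window whether or not a later event occurred. If A subjects have an event in the first window and B in the second, the number with an event from Treatment Period II onward is known only to lie between B - A and B.

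**Placebo/SYR-472 before and after the switch.** There are 84 readings before. After the switch there are 48 at once weekly (48/84 = 0.57, 43% fewer expected events), 89 at twice weekly (1.06, 6% more), or 294 if daily (3.5-fold).

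**Would a rate per patient-week over the whole window help?** Not enough: 132/54 = 2.44 against 48/42 = 1.14 readings per week, still 2.14-fold.

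**The case against.** The case against acting is substantial, and most of it stands.

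- **The table already separates Treatment Period I.** A reader might infer that it offers no balanced view of events after the switch. The documents do not support that: the balanced event totals follow from subtracting two planned cells. What remains is the subjects row.
- **The randomized comparison is sound.** A reader might infer that the trial's hypoglycemia comparison against placebo is distorted. It is not: both groups have 84 scheduled daily readings in Treatment Period I.
- **The table carries little inferential weight.** It is descriptive, concerns an additional endpoint and covers insulin users only. Hypoglycemia reported as an adverse event has its own listing (SAP 3.1.2, item 19) and enters the over-time display with an at-risk denominator (item 9). Those displays do not, however, cover the glucose-based classification in 3.3.2.3.
- **The ratio of 2.75 belongs to the minimum schedule.** Actual testing frequency is not given, and the ratio falls to 1.29 if subjects keep testing daily. This stands, although no frequency considered here removes the imbalance.

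A reader might also infer that the symptomatic rows are untouched because symptoms prompt their own tests. The protocol does not support so clean a line. Under 9.1.21 and 9.1.22, symptoms are also checked whenever a self-monitored value is 70 mg/dL or less, so a scheduled reading can give rise to a symptomatic event. The size of that effect cannot be worked out from the documents.

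**Conclusion.** The point holds as a minor one about presentation. For asymptomatic and all hypoglycemia, the after-SYR-472 columns compare 132 with 48 minimum scheduled readings per completer, and the table says nothing about it. Event totals can be put right by subtraction; the number of subjects with events cannot.

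The size rests on these assumptions: completion of follow-up, testing on the minimum schedule, equal risk per reading, and All hypoglycemia meaning Overall hypoglycemia as defined. Two things could move the counts. Item (i) of the scheduled-monitoring list in Protocol 9.1.21 was not legible in the text examined, and which readings are evaluable is left to the Handling Rules for Analysis Data. The percentages of subjects are illustrations at assumed risks, not forecasts.

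**What to change.** In SAP 3.3.2.3:

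1. Keep every planned row. The protocol calls for hypoglycemia after the start of SYR-472, and those counts should stay.
2. Add, by treatment group, the number of subjects and the number of events from the start of Treatment Period II study drug to the end of follow-up. The denominator is insulin users who started that drug. Both groups then have 7 + 41 = 48 minimum scheduled readings over 42 weeks. At an assumed 0.5% risk per reading, the same in every subject, both would show 21.4% of subjects with an event.
3. Add a footnote that scheduled testing changes from daily to at least weekly after Day 7 of Treatment Period II. For the asymptomatic and all-hypoglycemia rows, it should say that the whole after-SYR-472 columns are not directly comparable between groups, and that the placebo/SYR-472 before and after columns are not directly comparable either.

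The start of Treatment Period II is a better boundary than the day on which testing changes. A cut at Day 7/8 would leave a daily-phase cell of 91 against 7 readings. At 0.5% risk that is 36.6% against 3.4% of subjects with an event, a worse imbalance than the present row.

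The added rows need only event dates and the date of first Treatment Period II drug. A rate per reading would also need the normal readings in the database, and the protocol's recording rule, "The investigator or sub-investigator will record all applicable blood glucose values in the eCRFs", does not settle whether they are there.

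The cost is a few extra rows and one footnote in a descriptive table. Nothing changes in the testing schedule or in patient care. The added rows equalize scheduled testing only; extra testing in response to glucose levels may still differ between groups.

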4 SIGNIFICANCE LEVEL AND CONFIDENCE COEFFICIENT

- Significance level: 5% (two-sided tests)
- Confidence coefficient: 95% (two-sided)

History of Revision (version management)

Version	Date	Prepared/modified by	Comments
First Version	16 April 2018	PPD	Preparation of first version
Second Version	12 June 2018		Preparation of second version

[Appendix 1] SYR-472-3003 Comparison Table for Changes

Page	Existing Text	Revised Text	Rationale for Changes
18	
1.2.1 Distribution of Baseline Demographics
 
Rapid-acting insulin secretagogues [Yes]
 
...
 
α-glucosidase inhibitors [Yes]
 
...
 
Insulin preparations [Yes]
 
Mixed [Yes]
 
Intermediate-acting [Yes]
 
Long-acting soluble [Yes]
	
1.2.1 Distribution of Baseline Demographics
 
Rapid-acting insulin secretagogues [Yes, No]
 
Details of rapid-acting insulin secretagogues
 
...
 
α-glucosidase inhibitors [Yes, No]
 
Details of α-glucosidase inhibitors
 
...
 
Insulin preparations [Yes, No]
 
Types of insulin preparations [Mixed, intermediate-acting, Long-acting soluble]
	Adjustment of descriptions and changes in the contents of distributions as a result of reexamination of contents of distributions
19	
1.2.1 Distribution of Baseline Demographics
 
HbA1c (%) (Week 0)
 
[Min\leq - <8.0, 8.0\leq - \leqMax]
	
1.2.1 Distribution of Baseline Demographics
 
HbA1c (%) (Week 0)
 
[Min\leq - <7.0, 7.0\leq - \leqMax]
 
[Min\leq - <8.0, 8.0\leq - \leqMax]
	Addition of distributions as a result of reexamination of contents of distributions
20	
1.2.4 Concomitant Antidiabetic Drugs
 
Permitted in the Study
 
Any change in doses of antidiabetic drugs that are being used at Week -6 and will be concomitantly used during the study period in Treatment Period II
	
1.2.4 Concomitant Antidiabetic Drugs
 
Permitted in the Study
 
Any change in antidiabetic drugs that are being used at Week -6 and will be concomitantly used during the study period in Treatment Period II
	Adjustment of descriptions to clarify the contents of distribution

Page	Existing Text	Revised Text	Rationale for Changes
	
...
 
Also, regarding the presence or absence of any change in doses of antidiabetic drugs that are being used at Week -6 and will be concomitantly used during the study period in Treatment Period II, ...
	
...
 
Also, regarding the presence or absence of any change in antidiabetic drugs that are being used at Week -6 and will be concomitantly used during the study period in Treatment Period II, ...
	
27	
2.4.8 Examination of Subgroups
 
Duration of disease (months)
 
[Min≤ - ≤60, 60< - =Max]
 
Fasting C-peptide (ng/mL)
 
[Min≤ - <1.0, 1.0≤ - <2.0, 2.0≤ - ≤Max]
	
2.4.8 Examination of Subgroups
 
Duration of disease (months)
 
[Min≤ - ≤120, 120< - =Max]
 
Fasting C-peptide (ng/mL)
 
[Min≤ - <2.0, 2.0≤ - ≤Max]
	Changes in the contents of distributions as a result of reexamination of categories at the blinded review
29	
3.1.2 3.1.2 Displays of Treatment-Emergent Adverse Events
	
3.1.2 3.1.2 Displays of Treatment-Emergent Adverse Events
 
(19) Hypoglycemia-related TEAEs by SOC and PT
	Addition of distributions as a result of reexamination of contents of distributions
